2. PROTOCOL SUMMARY

2.1. Synopsis

PRODUCT NAME/NUMBER	SB-121
PROTOCOL NUMBER	SBI-SB121-20-01
DEVELOPMENT PHASE	Phase 1
PROTOCOL TITLE	Randomized, Double-blind, Placebo-controlled, 28-Day Daily-dose Crossover Study of the Safety and Tolerability of SB-121 (Lactobacillus reuteri with Sephadex® and Maltose) in Subjects, ages 15 to 45 years, diagnosed with Autistic Disorder.
INDICATION	Treatment of autistic disorder
OBJECTIVES	
Primary Objective:
 
 • To evaluate the safety and tolerability of multiple doses of SB-121 in subjects with autistic disorder 
Secondary Objectives:
 
 • To monitor the elimination of Sephadex® from the GI tract in subjects with autistic disorder • To assess the impact of multiple doses of SB-121 on circulating oxytocin levels in subjects with autistic disorder • To assess the impact of multiple doses of SB-121 on tests of autistic disorder (AD) • To evaluate biomarkers of microbiota function, immune modulation, and inflammation following multiple doses of SB-121 in subjects with autistic disorder
STUDY DESIGN	
This is a phase 1, single-center, randomized, double-blind, placebo-controlled cross-over study to evaluate the safety and tolerability of 28-days of once daily oral administration of a preparation of L. reuteri with Sephadex® and maltose (SB-121), to subjects with autistic disorder
 
Up to 16 eligible subjects will be randomly allocated in a 1:1 ratio to receive treatment with either SB-121 or placebo. The investigational product will be provided to subjects in 2 bottles, the contents of which will be combined, allowed to sit for a period of 15-45 minutes and then added to a predefined drink. Subjects will undergo screening within ~14 days before administration of the investigational product (IP). All subjects will be required to provide written informed consent before any study-specific procedures are performed. Subjects will also be asked to provide consent to allow bio-banking of biological samples for future analysis. Subjects' eligibility for the study will be determined at Screening by assessment of inclusion and exclusion criteria. Eligible subjects will be provided with a stool sampling kit to collect a pretreatment stool sample within 48 hours before receiving the IP (timing of collection determined by the frequency of the subject's bowel movements).
 
Subjects will return to the study site on Day 1. Following confirmation of eligibility criteria, they will be randomized to receive SB-121 or placebo.

	
Following baseline tests, all subjects will be given their first dose of either SB-121 or placebo at the clinic then receive an additional 30 oral doses of SB-121 or placebo to be administered once daily at home, according to the treatment group they were randomized to. Refer to the Daily Medication Instructions for additional details.
 
Subjects will undergo study-specific procedures on Day 1 in accordance with the Schedule of Events. Vital signs will be measured and ECG will be collected before administration of the IP. Vital signs will be measured post-dose. Subjects will be discharged after all Day 1 evaluations have been completed.
 
Following the approximately 2-week washout period, all subjects will cross-over to the other treatment (SB-121 or placebo) and receive 30 oral doses to be administered once daily.
 
Subjects will be instructed to collect a total of 5 stool samples at home according to the following schedule:
 
• A pretreatment stool sample within approximately 48 hours before receiving the first dose of the IP.• Post-treatment samples:
◦ Sample 1 should be taken no sooner than 21 days or later than 28 days into the first treatment period of the study (prior to the completion of the first treatment period)◦ Sample 2 should be taken approximately 7 days into the washout period after the first treatment period of the study and before the second treatment period◦ Sample 3 should be taken no sooner than 21 days or later than 28 days into the second treatment period of the study (prior to the completion of the second treatment period)◦ Sample 4 should be taken approximately 7 days after the completion of the second treatment period of the study 
Subjects will be provided with sampling kits to collect stool samples at home. Kits will include labels for sample containers, which should be completed with the time and date that the sample was obtained. Subjects will be instructed to return all stool samples to the responsible laboratory using pre-labeled shipping containers; alternative strategies for returning stool samples can also be discussed between the investigator and subjects.
 
Subjects will be advised to contact the study site immediately in the event of symptoms consistent with bacteremia (e.g., fever, chills, diaphoresis) and to obtain appropriate medical care as indicated. In the event that subjects develop symptoms consistent with bacteremia, two blood samples will be collected, when feasible, for blood cultures and microbial identification.
 
Follow-up visits will be conducted on Day 28, Day 1 of treatment period 2 and Day 28 of treatment period 2 (see 2.2 Schedule of Events). Details of AEs occurring throughout the study will be collected by study staff at each visit. Weekly telephone calls will be conducted by the investigator or designee between in-person visits during each treatment period. These calls will record and evaluate adverse events and will also determine IP compliance. In the case of adverse events identified during a phone call, the investigator or designee may determine that an unscheduled in-person study visit and/or lab tests may be required. Gastrointestinal events (nausea, vomiting, diarrhea, constipation,

--	---

		abdominal distention, abdominal pain/cramps, and flatulence) and systemic events (fever, chills, and diaphoresis) occurring at any time during the study and within 2 weeks after the last dose of IP will be considered AEs of special interest (AESIs).
PLANNED NUMBER OF SUBJECTS	OF	The study will enroll up to 8 subjects in each group, for a total of up to 16 subjects.
STUDY CRITERIA	ENTRY	
Inclusion criteria
 
A subject will be eligible for study participation if he or she meets all of the following criteria:
 
 1. Subject and parent, caregiver or legally authorized representative has provided written informed consent for the study. 2. Subject is a male or female ≥ 15 and ≤ 45 years of age. 3. Diagnosis of Autistic Disorder as confirmed by gold standard clinical interview using DSM-5 criteria and administration of the Autism Diagnostic Observation Schedule-2 4. Subject, if female and of childbearing potential, is not lactating and not pregnant 5. Subject, if female, is either not of childbearing potential or is practicing an acceptable effective method of birth control. 6. Subject is willing to comply with all study requirements (including the requirements for stool sampling and biobanking) and to return to the study facility for the follow-up evaluations, as required. 
Exclusion criteria
 
A subject will be excluded from the study if he or she meets any of the following criteria:
 
 1. Subject has known allergy or significant adverse reaction to L reuteri, Sephadex®, maltose, or related compounds. 2. Subject has previously had GI surgery, intestinal obstruction, Clostridium difficile infection or diverticulitis. 3. Subject has travelled outside of the USA in the 30 days prior to screening. 4. Subject has had a diarrheal illness in 30 days prior to screening. 5. Subject currently has a fever or active/uncontrolled GI symptoms (e.g., nausea, vomiting, diarrhea, constipation, abdominal distention, abdominal pain/cramps, flatulence) or has had these within 14 days prior to screening. If the GI symptoms are stable, in the opinion of the investigator, the subject can be enrolled. 6. Subject has any immunological/autoimmune disorder including, but not limited to, systemic lupus erythematosus, rheumatoid arthritis, Sjögren's syndrome, inflammatory bowel disease, or immunoglobulin-deficiency disorder, that would increase the risk to the subject or interfere with the evaluation of SB-121. 7. Subject has a documented history of HIV, hepatitis B and/or hepatitis C 8. Subject has implanted prosthetic devices including prosthetic heart valves.

	
9. Subject has taken, or is taking, any of the following prohibited medications:
 
 Proton pump inhibitor within 2 weeks prior to screening Use of supplemental probiotics within 2 weeks prior to screening except for yogurt Current use of immunosuppressive medications, including corticosteroids Treatment with monoclonal antibodies within 4 weeks prior to screening Systemic antibiotics within 2 weeks prior to screening 
10. Subject has diabetes mellitus or is pre diabetic.
 
11. Subject has received any IP (or investigational device) within 30 days prior to screening
 
12. Subject has any of the following laboratory test results at Screening:
 
 absolute neutrophil count of $<1.5 \times 10^9/L$ alanine aminotransferase or aspartate aminotransferase $>1.5 \times$ upper limit normal (ULN), total bilirubin $>1.5 \times$ ULN (subjects with known Gilbert's Syndrome can be included) serum creatinine $>1.5 \times$ ULN any other abnormal laboratory test that is clinically significant in the judgment of the investigator. 
13. Subject has an unstable medical condition or is otherwise considered unreliable or incapable, in the opinion of the investigator, of complying with the requirements of the protocol.
 
14. Subject tests positive for drugs of abuse in a urine drug screen at screening.
 
15. Subject has a history of alcohol abuse.

INVESTIGATIONAL PRODUCT	Name: SB-121 (L. reuteri) [REDACTED]
REFERENCE PRODUCT	[REDACTED]
TREATMENT REGIMENS	
Eligible subjects will receive one dose of SB-121 or placebo daily for 28 days according to the treatment group to which they are allocated. 27 doses will be provided to the subject, prepared at home and combined with approximately 1 cup of a predefined drink. The first dose of IP will be administered at the clinic.
 
Subjects will be required to refrain from using additional probiotics (except for yogurt) for the duration of their study involvement.

PLANNED STUDY SITES	The study will be conducted at a single study site: Cincinnati Children's Hospital (CCH), [name]

CRITERIA FOR EVALUATION	
Primary endpoints:
 
 • Incidence and severity of treatment-emergent AEs (TEAEs), serious AEs (SAEs), AESIs, and AEs leading to discontinuation from the study • Incidence of presence of Sephadex® microspheres in the stool • Incidence of symptomatic bacteremia with positive L. reuteri identification 
Secondary endpoints:
 
Change from baseline in:
 
 • Clinical Global Impressions Severity and Improvement Subscales • Vineland Adaptive Behavior Scales (3rd edition) • Aberrant Behavior Checklist • Woodcock Johnson 3rd Edition • Repeatable Battery for Assessment of Neuropsychological Status • Test of Attentional Performance for Children (KiTap) • Neurophysiology Measures including EEG resting state, auditory habituation, and chirp modulated sweep auditory evoked response • Eye Tracking • Biomarkers in stool and blood samples: Plasma oxytocin, plasma vasopressin, serum hs-CRP, tumor necrosis factor-α, and stool biomarkers.
STATISTICAL METHODS	Summary statistics will be provided for the various parameters assessed during the trial. This will include summaries of AEs by severity and relationship to IP, changes from baseline in the AD measures, as well as changes from baseline in biomarkers.
SAMPLE SIZE DETERMINATION	The sample size was not determined based on statistical assumptions. Evaluation of up to 8 subjects per treatment group (16 subjects total) was considered sufficient to allow evaluation of the study's objectives.
STUDY AND TREATMENT DURATION	
The overall study duration is expected to be approximately 14-weeks.
 
The planned sequence and duration of the study periods will be as follows:
 
 1. Screening: Up to 14 days 2. Study Period 1: Approximately 28 days 3. Approximately 14-day washout period 4. Study Period 2: Approximately 28 days 5. Post-treatment: Up to 14 days 
The maximum study duration for each subject is approximately 98 days.

PROTOCOL DATE	09 August 2021

2.2. Schedule of Events

Measure	Study Period 1						WASH OUT (14-21 Days)		Study Period 2			Post-trial Washout	
	Day -14 to 0	Day 1	Day 7	Day 14	Day 21	Day 28	Day 35	Day 1*	Day 7	Day 14	Day 21	Day 28 (± 3)	Day 42 (± 4)
Screen	Visit 1: Pre-dose	Visit 1: Post-dose	Follow-Up 1: Phone	Follow-Up 2: Phone	Follow-Up 3: Phone	Visit 2: Final Visit of Period 1	Wash out period call	Visit 3: Visit Pre-dose	Visit 3: Post-dose	Follow Up 1: Phone	Follow Up 2: Phone	Follow Up 3: End-of-Study/Early Termination Visit	
Informed Consent	X												
Med/Psych Hx	X												
Physical Exam ^a	X							X	X				X
Safety Labs ^b	X							X	X				X
Pregnancy Test (females)	X	X						X	X				X
Biomarker Blood Draw	X							X	X				X
Vital Signs	X	X	X					X	X				X
ADOS-2 ^c	X												
DSM-5 Checklist	X												
WASI-II		X											
SCQ		X											X
CGI-S		X						X	X				X
CGI-I								X					X
Vineland-3		X						X	X				X

	Day -14 to 0	Day 1	Day 7 (+/-2)	Day 14 (+/-2)	Day 21 (+/-2)	Day 28 (+/-3)	Day 35 (+/-2)	Day 1	Day 7 (+/-2)	Day 14 (+/-2)	Day 21 (+/-2)	Day 28 (+/-3)	Post-trial Washout	
Measure	Screen	Visit 1: Pre-dose	Visit 1: Post-dose	Follow-Up 1 Phone	Follow-Up 2 Phone	Follow-Up 3 Final Visit of Period 1 Phone	Visit 2: Final Visit of Period 1	Wash out period call	Visit 3: Post-Pre-dose	Visit 3: Post-Pre-dose	Follow Up 1 Phone	Follow Up 2 Phone	Follow Up 3 Phone	Visit 4: End of Study/Early Termination Visit
ABC		X					X		X					X
ECG ^a	X	X					X		X					X
EEG/ERP/Chi rp	X						X		X					X
Eye tracking		X					X		X					X
WJ3 Subtests		X					X		X					X
RBANS		X					X		X					X
KITap		X					X		X					X
IP Compliance											X	X	X	
AE Review			X	X	X	X			X	X	X	X	X	
Concomitant Medication Review	X	X		X	X	X			X	X	X	X	X	X
Stool Sample			X ^c					X	X ^c			X	X ^c	

- a) A full physical exam will be done at screening. A limited focused physical exam may be done in case of adverse events at all other visits, as determined by the investigator
- b) Safety labs will include hematology, chemistry and urinalysis

- c) ADOS 2 results can be obtained from the medical record and used for the study if completed within the previous 36 months. If results for the ADOS are available, it will not be completed.
- d) ECG will be done at either the screening or baseline visit for participants with AD.
- e) This is a pretreatment stool sample, to be collected within approximately 48 hours before receiving the first dose of the IP.
- f) Should be taken approximately 7 days into the wash-out period after the first treatment period of the study and before the second treatment period
- g) This is post treatment stool sample, to be collected approximately 7 days after the completion of the second treatment period of the study
- h) Study Period 2 Begins on Day 42 of the study or up to 7 days later

ADOS-2= Autism Diagnostic Observation Schedule Modules 2, 3 or 4; WASI-II= Wechsler Abbreviated Scale of Intelligence Scale-Second Edition, SCQ= social communication questionnaire; CGI-S= clinical global impressions severity scale, CGI-I=clinical global impressions improvement scale; Vineland-3= Vineland Adaptive Behaviors Scales 3rd edition; PK= pharmacokinetics; EEG= electroencephalogram protocol; WJ3= Woodcock Johnson Spatial Relations and Auditory Attention subtests; RBANS= repeatable battery of neuropsychological status; KiTap= computerized test of attentional performance in children; ABC= aberrant behavior checklist;

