7. STUDY DESIGN

7.1. Overall Study Design and Plan

This is a phase 1, single-center, randomized, double-blind, placebo-controlled cross-over study to evaluate the safety and tolerability of 28-days of once daily oral administration of SB-121 (a preparation of *L. reuteri* with Sephadex® and maltose), to subjects with AD.

Up to 16 eligible subjects will be randomized 1:1 to receive treatment with either SB-121 or placebo for 28 days. After a washout period of ~14 days, the subjects will be crossed over to the alternate treatment for 28 days.

Subjects will undergo screening within ~14 days before the first administration of the investigational product (IP). All subjects (or parent/authorized designee) will be required to provide written informed consent before any study-specific procedures are performed. Subjects will also be asked to provide consent to allow storage of biological samples for future analysis that will not involve genetic tests. Subjects' eligibility for the study will be determined at Screening by assessment of inclusion and exclusion criteria. Eligible subjects will be provided with a stool sampling kit to collect a pretreatment stool sample within 48 hours before receiving the IP.

Subjects will return to the study site (clinic) on Day 1. Following confirmation of eligibility criteria, they will be randomized to receive SB-121 or placebo. Following baseline tests, all subjects will be given their first dose of either SB-121 or placebo at the clinic.

Subjects will undergo study-specific procedures on Day 1 in accordance with the schedule of events and will be discharged after all Day 1 evaluations have been completed. They will then take the IP at home once a day for the remaining 27-days. They will then return to the clinic on Day 28.

Following the ~14 day washout period, all subjects will cross-over to the other treatment (SB-121 or placebo) for 28-days and the study procedures will be repeated.

Subjects will be instructed to collect a total of 5 stool samples at home according to the following schedule:

- A pretreatment stool sample within approximately 48 hours before receiving the first dose of the IP.
- Post-treatment samples:
 - Sample 1 should be taken no sooner than 21 days or later than 28 days into the first treatment period of the study (prior to the completion of the first treatment period)

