10.2.3 Treatment Visit – Day 1 (See Schedule of Events Section 2.2)

Following confirmation of eligibility criteria, subjects will be randomized to receive SB-121 or placebo. Subjects will undergo study-specific procedures on Day 1 in accordance with the Schedule of Events.

Following baseline tests, all subjects will be given their first dose of either SB-121 or placebo at the clinic. The IP will be prepared according to the provided Daily Medication Instructions.

All subjects receive an additional 27 doses of IP to be self-administered once daily at home at about the same time every day (e.g. around breakfast). In addition to the 27 oral doses, additional material will be provided for use in the event of spillage. Refer to the Daily Medication Instructions

for details on IP storage, reconstitution and consumption. All subjects will be instructed to capture the date and time of each dose of IP on the Patient Diary.

Subjects will be discharged after all Day 1 evaluations have been completed.

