5.1.2. Screening / Baseline Period

For all subjects, the screening period will be defined as the period from informed consent to the first dose of treatment in Treatment Period 1.

Baseline values for analyses of Treatment Period 1 will be the last observation prior to dosing in Period 1. Baseline values for analyses of Treatment Period 2 will be the last observation after the Treatment Period 1 washout and prior to dosing in Treatment Period 2. An additional analysis will be done for change of certain parameters, as discussed in Section 6.1, to the end of Treatment Period 1 and to the end of Treatment Period 2, respectively, utilizing as Baseline values the last observation prior to dosing in Treatment Period 1. This will be done for each treatment group.

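### The synopsis study design gives 31 doses in Period 1 and 30 in Period 2, against the 28 per period stated elsewhere; the Day 42–49 crossover rule is right for 28 doses but has no floor tied to the last dose

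*Protocol*

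**What the plan says.** **Dose counts.** The Study Design row of the synopsis (Protocol 2.1) describes a first dose in the clinic, after which subjects "then receive an additional 30 oral doses of SB-121 or placebo to be administered once daily at home". For the second period it says they "receive 30 oral doses to be administered once daily". Three other places describe a shorter regimen:

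- Synopsis, Treatment Regimens row: daily dosing for 28 days, the first dose in the clinic, and "27 doses will be provided to the subject".
- Section 7.1: after Day 1, "They will then take the IP at home once a day for the remaining 27-days".
- Section 10.2.3: a further 27 home doses after the clinic dose. On spare supply it adds: "In addition to the 27 oral doses, additional material will be provided for use in the event of spillage".

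The protocol title and section 5.4.1 also describe 28 days of dosing, and SAP 2.1 says approximately 28.

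**Crossover timing.** The header of the Schedule of Events (Protocol 2.2) reads "WASH OUT (14-21 Days". Footnote h to the same schedule says "Study Period 2 Begins on Day 42 of the study or up to 7 days later". Visit 2, which closes Period 1, is set at Day 28 with a window of 3 days either side. The narrative text calls the washout approximately 14 days or 2 weeks.

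**Use in the analysis.** SAP 5.1.2 takes the Period 2 baseline as "the last observation after the Treatment Period 1 washout and prior to dosing in Treatment Period 2".

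**The concern.** Two rows of one synopsis prescribe different numbers of doses, and the Study Design row does not agree with itself across the two periods. This is the first study of SB-121 in humans (Protocol 5.3) and safety is the primary objective, so planned exposure per period should have a single value. Protocol 13.1.2.2 lists dosing errors as possible major deviations. A site cannot classify a 29th dose as an error or as correct dosing when the protocol supports both answers.

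The dose count also bears on the washout. Footnote h is tied to the study day and not to the last dose. If a subject took 31 daily doses, the last would fall on Day 31, and a Day 42 start would meet footnote h while falling short of the schedule's own 14-day minimum. A late Visit 2 could have the same effect, because no passage says whether dosing stops on Day 28 or continues to a visit held on Day 29, 30 or 31.

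**Working it through.** **Step 1. Dose counts.** Doses in a period = clinic dose + home doses.

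| Source | Period 1 | Period 2 | Total |
|---|---|---|---|
| Synopsis, Study Design | 1 + 30 = 31 | 30 | 61 |
| Synopsis Treatment Regimens; 7.1; 10.2.3 | 1 + 27 = 28 | 28 | 56 |
| Difference | 3 (3/28 = 10.7%) | 2 (2/28 = 7.1%) | 5 (5/56 = 8.9%) |

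With daily dosing from Day 1, 28 doses end on Day 28 and 31 doses end on Day 31.

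**Step 2. Reproduce the stated washout.** Interval = study day of the first Period 2 dose − study day of the last Period 1 dose (L). Footnote h allows Days 42 to 49. With L = 28:

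- earliest start: 42 − 28 = 14
- latest start: 49 − 28 = 21

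This matches the header's 14–21 days exactly, so footnote h is arithmetically correct for the 28-dose regimen.

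**Step 3. Vary the last dose over the Visit 2 window (Days 25–31).**

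| L | Interval at Day 42 | Interval at Day 49 | Permitted starts giving less than 14 days |
|---|---|---|---|
| 25 | 17 | 24 | none |
| 26 | 16 | 23 | none |
| 27 | 15 | 22 | none |
| 28 | 14 | 21 | none |
| 29 | 13 | 20 | Day 42 |
| 30 | 12 | 19 | Days 42–43 |
| 31 | 11 | 18 | Days 42–44 |

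The 14-day minimum holds for every last dose on or before Day 28. Last doses on Days 25–27 can only exceed the 21-day upper limit. For L = 31, three of the eight permitted starts fall short (11, 12 and 13 days) and five comply (Days 45–49, giving 14 to 18). The largest shortfall is 14 − 11 = 3 days, or 3/14 = 21% of the minimum.

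**Step 4. Does the planned dose count enter the analysis?** SAP 6.5 divides kits used by the actual days on treatment times the kits prescribed per day. SAP 6.7.1 derives exposure from the actual first and last dose dates, less off-treatment days. Neither formula uses a planned number of doses. For a fully adherent subject who uses no spare kits, compliance is 28/28 or 31/31, 100% either way. The discrepancy does not distort the compliance figure, but that figure would not reveal it either.

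**The case against.** The strongest defence of the dose count is that the 30 is a supply figure: 27 home doses plus 3 spares. If so, the last dose is on Day 28 and there is no shortfall. This is possible, but the text does not support it. The Study Design row does not mention spillage and describes the doses as ones to be administered daily, while section 10.2.3 counts spillage material on top of the 27 and gives no amount. Even as a supply figure, the sentence would mislabel what it counts. The Daily Medication Instructions may give the right number, but they are not among the documents.

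The defence of the washout is stronger, and most of it stands. Footnote h is correct for the intended regimen. The 14–21 day header sits in the same schedule, so a site that follows both rules cannot start on Day 42 after a Day 31 dose; it would start on Days 45–49, which footnote h allows. Much else points to Day 28 as the end of dosing: the title, stool Sample 1 due by Day 28 and before the period is complete, SAP 5.1.3 closing Period 1 at Visit 2/Day 28, and a 98-day maximum equal to 14 + 28 + 14 + 28 + 14.

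A reader might infer that the crossover rule is miscalculated, or that subjects will cross over after an inadequate washout and so bias the Period 2 baseline. The documents support neither. The arithmetic in footnote h is right, no passage shows that 11 days is too short, and the Period 2 baseline is defined whatever the interval.

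**Conclusion.** The dose-count conflict is real, and the Study Design row of the synopsis is wrong as written: 31 and 30 doses where the regimen is 28 and 28. The error sits in an operative description of dosing, so it should be corrected.

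The washout point is secondary and conditional. An interval below 14 days needs a last dose on Day 29, 30 or 31, either because the Study Design row is followed literally or because dosing continues to a late Visit 2. It also needs a start on one of the earliest permitted days, against the schedule header. The lowest value is then 11 days.

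Assumptions: once-daily dosing from Day 1 with no doses held as spares, and the interval counted as start day minus last-dose day. That is the convention under which the protocol's own figures agree; counting fully dose-free days gives one fewer in each case. Severity is minor: no bias is shown and no SAP formula depends on the planned count.

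**What to change.** 1. In the Study Design row of the synopsis, give 28 doses in each period (1 in the clinic plus 27 at home), and label any extra units as spillage material.
2. Add one sentence stating that dosing stops on Day 28 even if Visit 2 takes place on Day 29–31.
3. In footnote h, keep the Day 42–49 rule and add: *and not less than 14 days after the last Period 1 dose*.

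The study-day rule should not be replaced by a 14–21 day count from the last dose. That would permit Days 39–46 after a Day 25 last dose (25 + 14 to 25 + 21) and Days 45–52 after a Day 31 last dose (31 + 14 to 31 + 21), outside the planned window at both ends. Adding a floor avoids this: even for a Day 31 last dose, Days 45–49 remain available.

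The cost is two corrected dose counts, one new sentence and one added clause. No new data are needed, because dose dates go into the Patient Diary (Protocol 10.2.3) and first and last treatment dates are already listed under SAP 6.7.1. At most, a Period 2 start moves from Day 42 to Day 45.
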